### **9.6.2.2. Tipping Point (Region) Approach**

The primary endpoint will also be analyzed using a special application of multiple imputation of missing values known as the tipping point method. The tipping point method assesses the possibility that subjects on active drug with missing values have worse outcomes than subjects on placebo. This sensitivity analysis involves multiple imputations and is also under the MNAR assumption in which one searches for a tipping point (region) that reverses the study conclusion. This approach is iterative in nature which tests how severe departures from MAR must be in order to overturn conclusions from the primary analysis. If these departures from MAR in order to change the results from statistically significance ( $p \leq 0.05$ ) to statistically insignificance ( $p > 0.05$ ) are deemed to be implausible, the results will be said to be robust to the departure from MAR assumption.

The tipping point approach will be applied to the analysis of the primary endpoint using the MMRM. In the MMRM, the dependent variable is change from baseline while the covariates are treatment, site, baseline value and study day as the within-subject effect.

The imputation will be done on the missing cases of change from baseline values for GSP304 treatment and Spiriva. Under the MNAR assumption, the imputed values for observations in the active treatment group and Spiriva, as well as placebo, will be adjusted directly using a shift parameter. Missing values are imputed under the assumption that the distribution of the missing observations has a lower expected value than that of the observed only by a shift parameter value. The maximum shift parameter is set at 80 mL for being about 50% of treatment efficacy when assuming that a difference in mean change from baseline at the end of treatment in trough FEV1 between GSP304 and GSP304 placebo is 150 mL. The shift parameter will take on the values from -80 mL to 0 with increment of 20 mL as it is assumed that the tipping point that will reverse the study conclusion is those values. If the tipping point is found to be between two increments on the given interval, a subsequent tipping point procedure will be performed using an interval on the neighborhood of the perceived tipping point finer increments for the shift parameter. If no tipping point is found, the shift parameter will be made more stringent and the process repeated.

Implementing the tipping point approach includes the following steps with the first three steps being the standard multiple imputation (MI) steps using SAS:

- a) The missing data are filled in  $m$  times to generate  $m$  complete data sets using PROC MI.
- b) The  $m$  complete data sets are analyzed using PROC MIXED.
- c) The results from the  $m$  complete data sets are combined for the inference using PROC MIANALYZE.

- d) Repeat the steps (a) to generate multiple imputed data sets with a specified shift parameter that adjusts the imputed values for observations in the active treatment and placebo groups.
- e) Repeat the step (b) for the imputed data sets with shift parameter applied.
- f) Repeat the step (c) to obtain the p-value to see if the p-value is still  $\leq 0.05$ .
- g) If needed, repeat the steps (d)-(f) with more stringent shift parameter applied until the p-value  $> 0.05$ .

The iteration for each value of the shift parameter will be summarized in a table where the estimated treatment differences for the treatment comparisons will be presented together with 95% confidence intervals for the differences and p-values for the treatment comparisons.

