### **4.3. Sample Size Considerations**

#### **4.3.1. Sample Size Justifications**

A sample size of 28 subjects per treatment arm will have 90% power to detect a difference in mean change from baseline in trough FEV1 of 150 mL between GSP304 and GSP304 placebo assuming a 2-sided alpha of 5% and a standard deviation (SD) of 170 mL. These assumptions are based on available literature from similar studies conducted for Spiriva® Respimat® (Caillaud et al., 2007). Given the overall 1:1:1:1:1 study treatment allocation ratio, 140 subjects are required for the analysis of the primary endpoint. Assuming a dropout rate of 10%, a total of 155 subjects (31 subjects per treatment arm) will be randomized.

This sample size is also considered to be sufficient for the relative bioavailability endpoint.

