LSMD = Least Square Mean Difference for each GSP304 vs placebo, and Spiriva vs placebo; The model will include trough FEV1 from all visits (Days 1, 6, 13, 20 and Day 21), and fixed terms for treatment, visit, center, baseline, treatment by visit and baseline by visit interactions; Unstructured covariance structure is used  
 LSMD = Least Square Mean Difference; N = Number of full analysis subjects;

Program location/program name.sas/ddmmmyyyy/hh:mm

Source Data: Listing xxxxxxx Database Extract Date: ddmmmyyyy

Programming notes:

Table 14.2.1.6  
 Sensitivity Statistical Analysis of Change from Baseline in Day 21 Trough FEV1(L) :  
 Tipping Point Approach

Full Analysis Set

Shift Parameter [1] for GSP304 xx ug (n=xxx)		Shift Parameter for GSP304 Placebo (n=xxx)				
	Statistics	0 mL	-20 mL	-40 mL	-60 mL	-80 mL
0 mL	LSMD	xx.x	xx.x	xx.x	xx.x	xx.x
	95%CI	(xx.x, xx.x)	(xx.x, xx.x)	(xx.x, xx.x)	(xx.x, xx.x)	(xx.x, xx.x)
	p-value	x.XXX	x.XXX	x.XXX	x.XXX	x.XXX
-20 mL	LSMD	xx.x	xx.x	xx.x	xx.x	xx.x
	95%CI	(xx.x, xx.x)	(xx.x, xx.x)	(xx.x, xx.x)	(xx.x, xx.x)	(xx.x, xx.x)
	p-value	x.XXX	x.XXX	x.XXX	x.XXX	x.XXX
-40 mL	LSMD	xx.x	xx.x	xx.x	xx.x	xx.x
	95%CI	(xx.x, xx.x)	(xx.x, xx.x)	(xx.x, xx.x)	(xx.x, xx.x)	(xx.x, xx.x)
	p-value	x.XXX	x.XXX	x.XXX	x.XXX	x.XXX
-60 mL	LSMD	xx.x	xx.x	xx.x	xx.x	xx.x
	95%CI	(xx.x, xx.x)	(xx.x, xx.x)	(xx.x, xx.x)	(xx.x, xx.x)	(xx.x, xx.x)
	p-value	x.XXX	x.XXX	x.XXX	x.XXX	x.XXX
-80 mL	LSMD	xx.x	xx.x	xx.x	xx.x	xx.x
	95%CI	(xx.x, xx.x)	(xx.x, xx.x)	(xx.x, xx.x)	(xx.x, xx.x)	(xx.x, xx.x)
	p-value	x.XXX	x.XXX	x.XXX	x.XXX	x.XXX

Trough FEV1 is defined as the average of FEV1 obtained 23 hours 15 minutes and 23 hours 45 minutes post-morning dose of the previous day.; N = Number of full analysis subjects; n = Number of subjects with at least one post baseline visit in the summarized category

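### SAP 9.6.2.2 contradicts itself and Table 14.2.1.6 on how placebo is imputed and shifted in the tipping-point analysis, and does not say which shifts decide tipping

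*SAP*

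**What the plan says.** Section 9.6.2.2 gives the purpose as follows: "The tipping point method assesses the possibility that subjects on active drug with missing values have worse outcomes than subjects on placebo".

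On which arms are imputed: "The imputation will be done on the missing cases of change from baseline values for GSP304 treatment and Spiriva". Placebo is not named. The next sentence nevertheless says that "the imputed values for observations in the active treatment group and Spiriva, as well as placebo, will be adjusted directly using a shift parameter".

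Step (d) of the implementation list repeats the imputation with "a specified shift parameter that adjusts the imputed values for observations in the active treatment and placebo groups". Steps (f) and (g) then look at the p-value and, if it is still at or below 0.05, make the shift more severe until it is not. The section closes by saying that a table will summarise the iteration for each value of the shift parameter. The planned values run from 0 to -80 mL in steps of 20 mL. Robustness is claimed if the departure needed to lose significance is judged implausible.

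The output shell, Table 14.2.1.6 in section 12.2, has the GSP304 shift in its rows and "Shift Parameter for GSP304 Placebo (n=xxx)" in its columns, each from 0 to -80 mL. That is a 5 x 5 grid of separate shifts. Its footnote again speaks of a single shift parameter and covers GSP304 versus placebo only.

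**The concern.** Three things do not fit together.

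- Placebo values cannot be shifted as imputed values if only GSP304 and Spiriva are imputed.
- The text and steps (d)-(g) read most naturally as one shift applied to active and placebo together, with one p-value per shift. The shell shows two shifts varied independently. A programmer could follow either.
- A common shift asks what happens if dropouts in every arm did equally badly. The stated aim asks what happens if active dropouts did worse than placebo. Only a shift that lowers active relative to placebo bears on that.

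This is one of two planned missing-not-at-random checks on the primary FEV1 endpoint, alongside Jump to Reference. If the deciding shifts are not fixed in advance, whether a marginal result is called robust can depend on a choice made after unblinding.

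**Working it through.** **Inputs from SAP 4.3.1.** "A sample size of 28 subjects per treatment arm will have 90% power". The target difference from placebo is 150 mL, the SD is 170 mL and the test is two-sided at 5%. Planned dropout is 10%, with 31 randomised per arm.

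**Reproducing the plan's figure.** SE = 170 x sqrt(2/28) = 45.4 mL on 54 df. A two-sample t calculation with 28 per arm gives 90.0% power for 150 mL, which matches the SAP. The smallest significant difference is 91.1 mL. This SE is used below.

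**Effect of the shifts.** Let f be the share of an arm imputed at Day 21 and s its shift. To first order,

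change in difference = f_active x s_active - f_placebo x s_placebo.

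With a common shift s this becomes s x (f_active - f_placebo).

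| Imputed, active / placebo | Active -80, placebo 0 | Both -80 | Active 0, placebo -80 |
|---|---|---|---|
| 10% / 10% | -8 mL | 0 mL | +8 mL |
| 10% / 20% | -8 mL | +8 mL | +16 mL |
| 20% / 10% | -16 mL | -8 mL | +8 mL |

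Positive values favour GSP304. The 10% is the SAP's dropout rate; the 20% is an assumption to show the range.

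**Can the choice reverse the reading?** Take 10% imputed in each arm.

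- Observed 95 mL, both arms at -80 mL: the difference stays 95 mL, t = 95/45.4 = 2.09, p = 0.041, not tipped.
- Observed 95 mL, active -80 mL and placebo 0 mL: 95 - 8 = 87 mL, t = 87/45.4 = 1.91, p = 0.061, tipped.
- Observed 150 mL, active -80 mL and placebo 0 mL: 142 mL, p moves from 0.0017 to 0.0029, not tipped under either choice.

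**Where an active-only series tips.** Shift needed = (91.1 - observed difference) / f_active.

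| Observed difference | 10% imputed | 20% imputed |
|---|---|---|
| 95 mL | -39 mL | -20 mL |
| 100 mL | -89 mL | -45 mL |
| 120 mL | -289 mL | -145 mL |
| 150 mL | -589 mL | -295 mL |

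**Cells in the shell.** Of 25 cells, 5 shift both arms equally, 10 lower active further and 10 lower placebo further. The placebo 0 mL column is the active-only series.

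**Simulation, conditional on the common-shift reading.** Assumptions that the SAP does not give: one earlier trough with correlation 0.7, 20 imputations, 31 per arm, and dropouts of 3 and 3 or of 3 active and 6 placebo. The runs have no true effect; those significant in favour of GSP304 were examined. With 3 and 3 dropouts, 38% tipped by -80 mL under an active-only shift and 7% under a common shift. With 3 and 6, the figures were 38% and 0%. The opposite imbalance was not simulated. These percentages illustrate one reading and do not describe the plan as a whole.

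**The case against.** A reader might infer that the shift simply cancels and that the check can hardly fail. The SAP does not support that, for four reasons.

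- The words common and equal do not appear. The text points to a table, and that table crosses separate shifts. The section title, with its reference to a region, also suits a two-way grid. Read with the shell, exact cancellation at equal dropout is confined to 5 of 25 cells, and the active-only column is already planned.
- Surviving to -80 mL does not establish robustness. The search continues until significance is lost, and the size of that departure is then judged.
- A common shift is not biased in one direction: if active loses more subjects, it works against GSP304.
- Much of the insensitivity up to -80 mL comes from low planned dropout, which allows only 8 mL of movement at 10% even when active alone is shifted. In the simulation, 62% of chance positives (100% - 38%) also survived the active-only shift to -80 mL.

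All four stand. It is also fair that step (a) calls for complete data sets, which implies that placebo is imputed, and that this is a sensitivity analysis in a phase 2 trial with unadjusted p-values.

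The inconsistency remains. The shell is a display without a decision rule, and its footnote still speaks of one shift. Steps (d)-(g) describe a search along one parameter and do not say which path through the grid to follow. Step (a) leaves the sentence limiting imputation to GSP304 and Spiriva contradicted.

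**Conclusion.** Wrong as written: section 9.6.2.2 contradicts itself on placebo imputation and conflicts with Table 14.2.1.6 on whether there is one shift or two. Under a common shift the analysis does not address its stated aim. The difference moves by 0 mL with equal dropout and by about 8 mL in either direction at -80 mL when one arm has 10% imputed and the other 20%. The shell's placebo 0 mL column does address the aim but is not named as deciding.

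The practical size is modest. The choice matters for marginal results, such as 95 mL (p = 0.041 against 0.061), and not for an effect near the planned 150 mL. The arithmetic is first order, takes SE 45.4 mL from the SAP's sample-size assumptions, and ignores covariate adjustment and between-imputation variance.

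**What to change.** In section 9.6.2.2 and the shell of Table 14.2.1.6:

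1. State that missing values in all arms, placebo included, are imputed under MAR before any shift is applied.
2. State that active and placebo shifts vary independently, as in the shell.
3. In steps (d)-(g), read the tipping point, and escalate beyond -80 mL if needed, along the active-only series with placebo at 0 mL. Report the other cells as supplementary.
4. Add Spiriva versus placebo to the shell, or remove Spiriva from the tipping-point text.

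The cost is wording, plus one more comparison in the shell if Spiriva is kept; the active-only cells for GSP304 are already planned. The downside is that a marginal result may tip at a smaller shift and look less robust than it would under a common shift.

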### **9.6.3. Exploratory Analysis**

If appropriate, a dose response model will be fitted to the primary endpoint to estimate the dose response relationship. Dose response models to be evaluated will include  $E_{max}$  (3-parameter) and linear models.

The  $E_{max}$  model will be fitted as follows:

$$\text{Endpoint} = E_0 + \frac{E_{max} \text{ Dose}}{\text{Dose} + ED50} + \varepsilon$$

where  $E_0$  = Response at dose 0,  $E_{max}$  = Maximum effect,  $ED50$  = Dose at which 50% of the maximum effect is reached and  $\varepsilon$  = Residual error.

The linear model will be fitted as follows:

$$\text{Endpoint} = E_0 + \beta \text{Dose} + \varepsilon$$

where  $E_0$  = Response at Dose 0,  $\beta$  = slope and  $\varepsilon$  = Residual error

Should these models not fit the data appropriately other models may be explored. For all of the models, baseline will be included as a covariate at  $E_0$ . However, baseline may be fitted at  $ED50$  or  $E_{max}$  for the  $E_{max}$  model depending on how the model fits the data best. Other covariates will be explored. Depending upon the adequacy of model fitting some parameters may need to be parameterized on the log scale (e.g. variance,  $ED50$ ,  $E_{max}$ ). The most appropriate model will be assessed visually, by evaluating the AIC and by looking at the residuals. To build confidence in the chosen model, the null model:

$$\text{Endpoint} = E_0$$

will also be fitted to the data and the p-value from a likelihood ratio test will be computed; i.e. the change in deviance (-2 Log Likelihood) between the chosen model and the null model will be compared to a chi-squared distribution with degrees of freedom equal to the difference in the number of parameters in the two models.

Dose response model parameter estimates, along with corresponding 95% confidence intervals, from the final dose response model will be presented.

## **9.7. Analysis of the Secondary Pharmacodynamics Endpoints**

The secondary endpoints are:

- Change from baseline in peak FEV1 within 12 hours post-dose on Day 1 and 21
- Change from baseline (Day 1) at Day 21 (Week 3) in trough FVC response at approximately 24 hours after the last dose (average of 23 hours 15 minutes and 23 hours 45 minutes post-dose measurements)
- Change from baseline in time-normalized area under the curve for FEV1 measured over 12 hours on Day 1 and 21
- Time to onset of response, defined as at least 12% and 200 mL increase in FEV1 within 12 hours of dosing on Day 1
- Time to achieving steady state as measured by FEV1 trough assessments
- Time to achieving steady state as measured by FVC trough assessments

The change from baseline for the secondary pharmacodynamics endpoint of change from baseline (Day 1) at Day 21 (Week 3) in trough FVC response at approximately 24 hours after the last dose (average of 23 hours 15 minutes and 23 hours 45 minutes post-dose measurements) will be analysed using the same model as described above for the analysis of the primary endpoint.

The change from baseline for the secondary pharmacodynamics endpoints of; Change from baseline in peak FEV1 within 12 hours post-dose on Day 1 and 21 and change from baseline in time-normalized area under the curve for FEV1 measured over 12 hours on Day 1 and 21 will be analyzed using a mixed-effect repeated measures (MMRM) model. This model will assume that any missing data is Missing at Random (MAR). The model will include data from Day 1 and Day 21 and fixed terms for treatment, visit, center, baseline, treatment by visit and baseline by visit interactions. If an interaction term is significant, further ad-hoc analysis may be conducted. Subject will be included as a random term to account for the correlation between repeated measurements within a subject, and unstructured covariance structure will be used. If the model fails to converge, alternative structures (CS) or removing terms will be investigated. The covariance structure that provides the best fit (as determined by the smallest AIC value) will be used. The adjusted means for each treatment and the estimated treatment differences for the

treatment comparisons will be presented together with 95% confidence intervals, along with p-values for the treatment comparisons. The adjusted means and estimated treatment differences for the treatment comparisons (each GSP304 vs placebo, total GSP304 vs placebo, and Spiriva vs placebo) will also be plotted, with corresponding 95% confidence intervals.

For the secondary endpoint of time to onset of response of both a 12% and 200 mL increase from baseline in FEV1, the unadjusted mean change from baseline and unadjusted percent mean change from baseline will be summarized for day 1. The unadjusted means will also be plotted over time, for day 1. For the secondary endpoints of time to steady state in FEV1 and FVC, the adjusted means from the MMRM model discussed above will be summarized by day (Days 1, 6, 13, 20 and 21) and also plotted over time.

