#### **Analysis of Secondary Pharmacodynamics Endpoints**

Analysis of secondary PD endpoints will be performed on the FAS.

Change from baseline in peak FEV1 within 12 hours post dose on Day 1 and Day 21: This endpoint measures the peak FEV1 from the serial readings taken through 12 hours post-dose and then calculates the change from baseline. The change from baseline will be analyzed using MMRM in a similar way to that of the primary endpoint to produce treatment differences for each dose of GSP304 versus GSP304 placebo.

Change from baseline (Day 1) at Day 21 (Week 3) in trough FVC response at approximately 24 hours after the last dose (average of 23 hours 15 minutes and 23 hours 45 minutes post-dose measurements) will be analyzed using MMRM in a similar way to that of the primary endpoint to produce treatment differences for each dose of GSP304 versus GSP304 placebo.

Change from baseline in time-normalized area under the curve for FEV1 measured over 12 hours on Day 1 and Day 21: The endpoint measures a series of FEV1 readings taken within 12 hours of dosing.

The trapezoidal rule will be used to calculate AUC0-12h and then normalized to the length of time. The change from

baseline will be analyzed using MMRM in a similar way to that of the primary endpoint to produce treatment differences for each dose of GSP304 versus GSP304 placebo.

All PD data will also be displayed in summaries and listings.

Time to steady-state: This is the time period from the first dose to two consecutive similar trough FEV1 or FVC measurements. The trough values will be tabulated and plotted by time for each active dose and placebo.

Time to onset of action (of both a 12% increase and 200 mL increase in FEV1 within 12 hours of dosing): This is the time period from the first dose to first onset of at least 12 percent and 200 mL improvement in FEV1 over the baseline value. The trough values will be tabulated and plotted by time for each active dose and placebo.

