## **9.2. General Considerations**

All tests will be 2-sided and at 5% level of significance unless otherwise stated.

In addition to the analyses described below, all endpoints will be summarized over time, by treatment, as appropriate.

All endpoints will also be listed by treatment and subject. The interpretation of results from statistical tests will be based on the FAS. The PP population will be used to assess the robustness of the results from the statistical tests based on the FAS. Unless otherwise stated, ‘treatment’ refers to treatment group as randomized, rather than based on the actual treatment received.

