## **10.9. Changes from Protocol**

The following changes from the protocol were made in the SAP.

1) The definition of the primary endpoint was clarified from change from baseline in trough forced expiratory volume in one second (FEV1) at 24 hours after the last dose of treatment on Day 21 in comparison with placebo to change from baseline (Day 1) at Day 21 (Week 3) in trough FEV1 response at approximately 24 hours after the last dose (average of 23 hours 15 minutes and 23 hours 45 minutes post-dose measurements).

2) The language used for definition of the secondary endpoint of change from baseline in trough FVC, and the associated analyses related to this endpoint, was modified to align it with the language that has been used for the primary endpoint.

3) The following secondary endpoints were added;

- Time to onset of response, defined as at least 12% and 200 mL increase in FEV1 within 12 hours of dosing on Day 1
- Time to achieving steady state as measured by FEV1 trough assessments
- Time to achieving steady state as measured by FVC trough assessments

4) Spirometry Effort Start Time: will use the first effort (Test 1) regardless of whether this is an acceptable effort or not. Instead of “start time of first spirometry effort” (per protocol), we are using the end time of the first spirometry effort.

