## Full Analysis Set

Statistics	GSP304				Spiriva R	
	(N=xxx) n (%)	(N=xxx) n (%)	(N=xxx) n (%)	Placebo (N=xxx) n (%)	5 ug (N=xxx) n (%)	Total (N=xxx) n (%)
Any Use	xx (xx.x)	xx (xx.x)	xx (xx.x)	xx (xx.x)	xx (xx.x)	xx (xx.x)
Number of Puffs (years)	n	xxx	xxx	xxx	xxx	xxx
	Mean (SD)	xx.x (x.xx)	xx.x (x.xx)	xx.x (x.xx)	xx.x (x.xx)	xx.x (x.xx)
	Median	xx.x	xx.x	xx.x	xx.x	xx.x
	Min; Max	xx; xx	xx; xx	xx; xx	xx; xx	xx; xx

N = Number of full analysis subjects; n = Number of subjects with data in the summarized category

Program location/program name.sas/ddmmmyyyy/hh:mm

Source Data: Listing xxxxxxx Database Extract Date: ddmmmyyyy

Table 14.2.1.1  
 Summary of FEV1 (L) Data by Visit, Time and Treatments

Full Analysis Set

Visit	Nominal Time	Statistics	GSP304			Spiriva R	
			(N=xxx)	(N=xxx)	(N=xxx)	Placebo (N=xxx)	5 ug (N=xxx)
Day 1	-45 min	n	xxx	xxx	xxx	xxx	xxx
		Mean (SD)	xx.x(xx.xx)	xx.x(xx.xx)	xx.x(xx.xx)	xx.x(xx.xx)	xx.x(xx.xx)
		Median	xx.x	xx.x	xx.x	xx.x	xx.x
		Min; Max	xx;xx	xx;xx	xx;xx	xx;xx	xx;xx
		n	xxx	xxx	xxx	xxx	xxx
	-15 min	Mean (SD)	xx.x(xx.xx)	xx.x(xx.xx)	xx.x(xx.xx)	xx.x(xx.xx)	xx.x(xx.xx)
		Median	xx.x	xx.x	xx.x	xx.x	xx.x
		Min; Max	xx;xx	xx;xx	xx;xx	xx;xx	xx;xx
		n	xxx	xxx	xxx	xxx	xxx
		Mean (SD)	xx.x(xx.xx)	xx.x(xx.xx)	xx.x(xx.xx)	xx.x(xx.xx)	xx.x(xx.xx)
Baseline [1]	5 min	Median	xx.x	xx.x	xx.x	xx.x	xx.x
		Min; Max	xx;xx	xx;xx	xx;xx	xx;xx	xx;xx
		n	xxx	xxx	xxx	xxx	xxx
		Mean (SD)	xx.x(xx.xx)	xx.x(xx.xx)	xx.x(xx.xx)	xx.x(xx.xx)	xx.x(xx.xx)
		Median	xx.x	xx.x	xx.x	xx.x	xx.x
	Change from Baseline	Min; Max	xx;xx	xx;xx	xx;xx	xx;xx	xx;xx
		n	xxx	xxx	xxx	xxx	xxx
		Mean (SD)	xx.x(xx.xx)	xx.x(xx.xx)	xx.x(xx.xx)	xx.x(xx.xx)	xx.x(xx.xx)
		Median	xx.x	xx.x	xx.x	xx.x	xx.x
		Min; Max	xx;xx	xx;xx	xx;xx	xx;xx	xx;xx
Day 2	30 min	n	xxx	xxx	xxx	xxx	xxx
		Mean (SD)	xx.x(xx.xx)	xx.x(xx.xx)	xx.x(xx.xx)	xx.x(xx.xx)	xx.x(xx.xx)
		Median	xx.x	xx.x	xx.x	xx.x	xx.x
		Min; Max	xx;xx	xx;xx	xx;xx	xx;xx	xx;xx
		n	xxx	xxx	xxx	xxx	xxx
	Change from Baseline	Mean (SD)	xx.x(xx.xx)	xx.x(xx.xx)	xx.x(xx.xx)	xx.x(xx.xx)	xx.x(xx.xx)
		Median	xx.x	xx.x	xx.x	xx.x	xx.x
		Min; Max	xx;xx	xx;xx	xx;xx	xx;xx	xx;xx
		n	xxx	xxx	xxx	xxx	xxx
		Mean (SD)	xx.x(xx.xx)	xx.x(xx.xx)	xx.x(xx.xx)	xx.x(xx.xx)	xx.x(xx.xx)

Glenmark Specialty SA  
 Statistical Analysis Plan - Protocol #GSP304-201

SEPT 12, 2017

		Median Min; Max	xx.x xx;xx	xx.x xx;xx	xx.x xx;xx	xx.x xx;xx	xx.x xx;xx
90 min	n	xxx	xxx	xxx	xxx	xxx	xxx

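### Time to onset needs a 12% and a 200 mL rise together, but the SAP plans only group means against each limit separately and never gives the joint time

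*SAP*

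**What the plan says.** The Technical Summary Report at the front of the SAP defines the endpoint as a time: "This is the time period from the first dose to first onset of at least 12 percent and 200 mL improvement" in FEV1 over baseline. Section 9.7 lists it with the same joint criterion ("Time to onset of response, defined as at least 12% and 200 mL increase in" FEV1) and limits it to 12 hours after dosing on Day 1. Section 10.9 shows that the SAP itself introduced it: "The following secondary endpoints were added", with time to onset first on the list.

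The analysis text in section 9.7 names the endpoint as "time to onset of response of both a 12% and 200 mL increase from baseline" in FEV1. It then plans that "the unadjusted mean change from baseline and unadjusted percent mean change from baseline will be summarized for day 1", with the unadjusted means plotted over Day 1. In section 12.2, Figure 14.2.1.1.1 shows percent change with a reference line at 12%, and Figure 14.2.1.1.2 shows change with a reference line at 200 mL. Figures 14.2.1.1.3 and 14.2.1.1.4 repeat the pair for the per-protocol set.

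The Technical Summary Report also gives a display instruction for this endpoint: "The trough values will be tabulated and plotted by time for each active dose and placebo".

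**The concern.** The endpoint is a time at which two conditions hold together. The planned output is two curves of group averages, each judged against one condition. A programmer who follows the plan exactly produces no onset time, no count of subjects who reach onset, and no treatment of subjects who never do.

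Without a prespecified rule, the onset time in the report would have to be chosen after the curves are seen. Section 2 says that decisions on the final analysis are made before database lock. What is at stake is how a secondary endpoint that the SAP chose to add is described, including any statement on how quickly each dose acts.

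**Working it through.** The SAP states no figure for this endpoint, so there is none to reproduce. The check compares the passages and then asks whether two mean curves can stand in for the joint time.

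**1. Does any part of the SAP supply the joint time?**
- Section 6.7 derives the 12-hour FEV1 area under the curve in full (6.7.7). It has no derivation of onset.
- Table 11 marks a summary table and a figure for onset. The display list in 12.1 has onset figures but no onset table.
- Table 14.2.1.1 ("Data by Visit, Time and Treatments") summarises values and change from baseline by reading. Its shell has no percent change and no onset time.
- Section 9.2 says "All endpoints will also be listed by treatment and subject". The footnotes of Listing 16.2.6.1 name trough FEV1, peak FEV1, FVC and the FEV1 area under the curve, but not onset. Section 12.1 has no listing of the serial readings from which a reader could rebuild it.
- The trough sentence in the Technical Summary Report cannot help. Trough is the mean of the readings at 23 h 15 min and 23 h 45 min, which lie outside the 12-hour window.

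**2. Where do the two limits agree?** They are equal when 0.12 × baseline = 200 mL, so baseline = 200/0.12 = 1,667 mL. Below 1.67 L the 200 mL limit binds, and above it the 12% limit binds. The binding limit therefore depends on each subject's baseline.

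**3. Can both means pass while nobody has onset?** Take two subjects (values chosen for illustration):

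| | Baseline | Rise | Percent | Meets both? |
|---|---|---|---|---|
| A | 1,200 mL | 180 mL | 180/1,200 = 15.0% | No, below 200 mL |
| B | 2,200 mL | 240 mL | 240/2,200 = 10.9% | No, below 12% |

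- Mean rise: (180 + 240)/2 = 210 mL, above 200 mL.
- Percent change of the mean: 210/1,700 = 12.4%, above 12%.
- Mean of the percents: (15.0 + 10.9)/2 = 13.0%, above 12%.

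Both figures would mark the time point, and neither subject has reached onset.

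**4. Is the percent curve itself fixed?** The title of Figure 14.2.1.1.1 describes percent change in the mean, while its axis note describes mean percent change. With a rise of 160 mL at baselines of 1.0 and 2.0 L, the first is 160/1,500 = 10.7% and the second is (16 + 8)/2 = 12.0%. One stays below the line and the other reaches it.

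**5. How noisy is a first-crossing rule?** As a pure assumption, take a true mean change of 0 and an SD of 170 mL at each reading (the SD is borrowed from the trough sample-size section). At baselines up to 1.67 L, the chance of meeting both limits at one reading is 1 − Φ(200/170) = 12%. There are 11 scheduled Day 1 readings up to 12 hours. The chance of at least one crossing runs from 12% if they are perfectly correlated to 1 − 0.88^11 ≈ 75% if they are independent.

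**The case against.** The best defence is that the endpoint was meant at group level. No passage says that onset is per subject, Table 11 plans no formal analysis for it, and the two figures share a time axis and mark each point at or above their limit. The first time marked on both would then be a group onset time. It is true that the SAP does not say per subject. But it does not state this reading rule either, and step 3 shows that the rule can mark onset when no subject meets both limits.

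Other parts of the defence carry some weight:
- The trough sentence looks like a slip carried over from the steady-state paragraph, and section 9.7 already replaces it with Day 1 means.
- Listing 16.2.6.1 also omits the time-to-steady-state endpoints, so the listing gap is not peculiar to onset.
- Percent change is promised in section 9.7, so its absence from the Table 14.2.1.1 shell is weak evidence.
- Section 6.2 allows tables to be added after the analysis, although a rule added then would not be prespecified.
- A single-crossing rule counts noise as onset (step 5), so a simple per-subject derivation is not enough alone.

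A reader might also infer a definite size from the 150 mL in section 4.3.1, for instance that the mean curve stays under 200 mL all day while a known share of subjects responds. The SAP does not support that. The 150 mL is a difference from placebo in trough FEV1, not a mean change within an arm. The SAP gives no placebo change, no Day 1 profile and no baseline distribution.

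**Conclusion.** The point holds: the analysis in section 9.7 does not estimate the endpoint that the same section defines. No derivation, table or listing supplies the time at which both limits are met, and the two mean curves cannot recover it because the binding limit changes at a baseline of 1.67 L.

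The 1.67 L crossover and the two-subject example rest on arithmetic alone. They show that the mean plots can mislead, not how often or by how much. The typical size cannot be derived from the SAP, and the noise figures of 12% to 75% are assumptions used only to shape the fix.

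A reader might take this as a threat to the trial's main conclusions. It is not: the endpoint is descriptive, and no planned test and no primary conclusion depends on it. It should be corrected because the SAP added this endpoint deliberately and does not deliver it.

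**What to change.** In section 9.7:
- Derive, per subject, the first scheduled Day 1 post-dose reading up to 12 hours at which FEV1 is both ≥ 1.12 × baseline and ≥ baseline + 200 mL.
- State one time origin. The Technical Summary Report counts from the first dose, while section 4.5 times readings from the end of dosing; the two differ by the nebulization time.
- Treat subjects without onset as censored at their last reading up to 12 hours.
- Report by arm, with placebo alongside, the number and percentage with onset and the median time, or that the median was not reached.
- Show onset confirmed at the next reading beside the single-reading result, because a single crossing picks up noise.

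Elsewhere, add the table to 12.1 and the onset time to a listing. Keep the mean plots as supportive and state which percent change they show. Remove the trough sentence for this endpoint from the Technical Summary Report.

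The cost is one derived variable with a confirmed version, one table and one listing column, all from spirometry already scheduled. After 2 hours, onset is resolved only to the 2-hour gap between readings.
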